- **Termination Criteria:** Participants may be terminated for any of the following: (a) completion of study; (b) participant request to exit or withdraw consent; (c) development of suicidal or homicidal ideation requiring hospitalization; (d) development of a systemic, medical, neurologic or psychiatric illness requiring treatment that would exclude participation; (e) clinical deterioration (see below); (f) non-compliance with study protocol requirements including refusing to consent to not driving for at least 24-hours after Lab Visit 2 (Acute Drug Challenge) due to day-time drug administration; (g) significant worsening of AUD symptoms that would require treatment; and (h) a positive pregnancy test. If alcohol tests are positive, participants will be given the option to reschedule. If breath tests are again positive, participation will be terminated.

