Measures of Alcohol and Other Substance Use: (1) Alcohol Use Disorders Identification Test (AUDIT)³², (2) Timeline Follow-back (TLFB)³⁰; (3) The Obsessive Compulsive Drinking Scale (OCDS)³³, (4) The Drinker Inventory of Consequences (Dr-InC)³⁴, (5) the CIWA-Ar²⁹, (6) Drinking Motives Questionnaire-Revised (DMQ-R)³⁵, (7) Drug Abuse Screening Test (DAST)³⁶, (8) Cannabis Use Disorder Identification Test (CUDIT)³⁷, and (9) the Fagerstrom Test for Nicotine Dependence (FTND)³⁸.

Measures of Psychiatric Symptoms and Personality: (1) Beck Depression Inventory (BDI-II)³⁹, (2) Beck Anxiety Inventory (BAI)⁴⁰, (3) Generalized Anxiety Disorder Questionnaire (GAD-7)⁴¹, (4) Beck Hopelessness Scale⁴², (5) Snaith-Hamilton Pleasure Scale (SHAPS)⁴³, (6) PTSD Checklist-Civilian Version (PCL-5)⁴⁴, (7) Life Events Checklist for DSM-5 (LEC-5)⁴⁵, (8) The Personality Inventory

for DSM-5 (PID-5)⁴⁶, and (9) Beck's Scale for Suicidal Ideation Lifetime (SSI)⁴⁷, (10) The Depression, Anxiety and Stress Scale (DASS-21)⁴⁸, (11) The Inventory of Depression and Anxiety Symptoms (IDAS-II)⁴⁹, (12) Childhood Trauma Questionnaire (CTQ)⁵⁰, (13) Anxiety Sensitivity Index (ASI), (14) Highly Sensitive Person Questionnaire (HSP).

Other Measures: (1) Pittsburg Sleep Quality Index (PSQI)⁵¹, (2) Health Questionnaire, (3) Demographic Questionnaire, (4) Intolerance of Uncertainty (IUS)⁵², (5) Contact Information Form, (6) Emotion Regulation Questionnaire (ERQ)⁵³, (7) Psychiatric Treatment History Form (clinician administered), (8) Medication History form (clinician administered); (9) Exclusionary Medication Checklist; (10) BMI Questionnaire.

Identifying and Monitoring Drug-Drug Interactions. The study physician will review the participant's self-report Health Questionnaire, self-report Exclusionary Medication Checklist, and clinician administered Medication History form prior to randomization in order to assess exclusionary criteria and identify potential drug-drug interactions. PI and the study physician will utilize Lexicomp to check drug-drug interactions and only interactions of minor severity will be allowed. Those found to have potential moderate or severe drug-drug interactions will be withdrawn from the study, consistent with study exclusionary criteria. Potential drug-drug interactions will continually be monitored throughout the duration of the study.

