Each morning for the 4-week medication trial period, subjects will be asked to complete a brief clinical assessment, sent directly to subjects' smartphones at 8:30am. The survey will capture: medication adherence (yes/no); timing of pill ingestion; time spent in bed and asleep; medication side-effects; number and timing of alcoholic beverages; alcohol craving; illicit substance use; mood; and new medication usage to monitor potential drug-drug interactions. If the survey is not completed, a reminder will be sent to the participant every 30 minutes for 150 minutes (5 total reminders). Responses will be collected, password-protected, and encrypted locally on smartphones.

Subjects who endorse medication side effects other than nighttime drowsiness will be contacted by the study physician for a review of symptoms and safety. Additionally, if subjects endorse taking new medications, the study physician will review the information and contact the subject if further information is needed. The study physician and PI will utilize Lexicomp to check drug-drug interactions and only interactions of minor severity will be allowed. Those found to have moderate or severe interactions will be withdrawn from the study, consistent with study exclusionary criteria.

Subjects will also be contacted if medication compliance falls below 80% or above 120%. At the final lab visit, subjects will be asked to bring their blister pack with them to verify compliance using the pill count method. Thus, medication compliance is tracked using both daily self-report, pictures, and objective pill count.

Post-Treatment Lab Visits. During the final days of the trial, subjects will return to the lab to repeat the lab protocol. Individuals enrolled in the BRAINS Group will come in for a separate visit to repeat the fMRI. At study conclusion, subjects will be debriefed and provided a list of AUD treatment referrals and resources.

Self-report Data Processing. All measures will be double entered, checked for discrepancies, and cleaned. Analyses will assume that 'missingness' occurred at random, with data imputed when necessary.

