other side-effects have an incidence between 1-10%. Rare but potentially serious side effects include: worsening of depression and increase of suicidal ideation, complex sleep behavior and sleep paralysis, and temporary weakness in legs. Taking a CNS depressant (e.g., benzodiazepines, opioids, some antidepressants and anxiolytics, other sleeping medication) increase the risk of side effects and should not be taken at the same time as suvorexant. Suvorexant should not be taken with grapefruit juice, as this may significantly increase the levels of medication in the blood. Suvorexant should not be taken unless individuals are able to stay in bed for a full night (at least 7 hours) before they must be active again. Individuals should also not drive, operate heavy machinery, or do other activities that require clear thinking immediately after taking suvorexant.

Co-I, [name], M.D., is a Board-certified psychiatrist and physician, and will be available during the Acute Drug Challenge and Drug Trial in order to evaluate and/or recommend further evaluation and treatment for the emergence of any adverse events/side effects. Participants taking psychoactive/psychotropic medications or medications that would interact with suvorexant will be excluded. Pregnant participants will be excluded from participation because there is insufficient data to assure safety of the fetus during suvorexant exposure. As well, female participants who are not using acceptable methods of contraceptives or abstinence will be excluded. In addition, nursing mothers will be excluded from the study because the extent to which suvorexant is concentrated and excreted in human breast milk is unknown. Participants will be fully debriefed following the study. During debriefing, any questions participants may have will be answered.

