11.0 Data and Safety Monitoring

- We have developed a formal data safety and monitoring plan to ensure the ongoing safety of participants (as well as the integrity of the study). The plan involves weekly meetings that will be used to communicate any concerns or issues with safety, confidentiality, or progress.
- Suicidal Ideation: The PI is a clinician and has extensive experience in the assessment of acutely depressed and anxious patient volunteers at screening and in the context of lab assessments. The PI routinely evaluates for suicidal ideation, behavior and risk, and will consult with and closely oversee the clinical monitoring and suicide assessment during the study. If suicidality is endorsed by a participant at any point during the assessment or experimental portion of the study, appropriate steps will be taken. Specifically, the PI or trained study staff member will a) obtain a more detailed assessment of intent, plan and method, including using the gold-standard, empirically-validated Columbia Suicide Severity Rating Scale (CSSRS)⁷⁰; b) discuss the situation with the participant, the participant’s emergency contact, and/or members of the mentorship team as warranted; c) consult with the PI and/or CO-Is; and d) make an appropriate treatment referral for the participant. If the PI believes that the participant is in imminent danger, they will call 911 or will walk the participant over to the emergency room at the Ohio State University hospital, only 1 block away.

- Once enrolled, participants who show deterioration between assessment and the lab tasks (e.g., increased anxiety, depression, mania, psychosis, or suicidality) may be removed from the study and referred to our outpatient psychiatry clinic or emergency psychiatric evaluation, if necessary. Participants who are deemed to be at high risk during either the assessment or experimental session may need to be psychiatrically hospitalized. If the CSSRS indicates suicidal thinking or if suicidal behavior is present, or if there is any concern about current suicide risk, the PI will evaluate suicide risk and decide what level of care is sufficient. The PI will then facilitate follow-up visit, Emergency Room/emergency department visit or inpatient admission if necessary.

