KSS			x (9 times)			
VAS			x (9 times)			
DEQ			x (9 times)			
POMS			x (4 times)			
Daily Clinical Assessment Form				x		

*CSSRS will be completed as necessary based upon participant reports of suicidal ideation.

Table 2. Administration of Questionnaires for BRAINS Group.

Interviews and Questionnaires	Screening Session	Lab Visit 1: Pre-Tx (EMG #1)	Lab Visit 2: Pre-Tx (fMRI #1)	Lab Visit 3: Acute Drug Challenge (EMG #2)	Daily Clinical Assessments	1-Month Follow-up	Lab Visit 4: Post-Tx (EMG #3)	Lab Visit 5: Post-Tx (fMRI #2)
SCID-5 Diagnostic Interview	x							
C-SSRS*	x							
Contact Information Form	x							
NIAAA GUID Information	x							
Health Questionnaire	x							
BMI Questionnaire	x							
Exclusionary Medication Checklist	x							
Medication History Questionnaire (clinician administered)	x							
Psychiatric Treatment History Form (clinician administered)	x							
Demographic Information Form	x							
BDI-II	x					x		
BAI	x					x		
SSI (timeframe: lifetime)	x							
IUS	x					x		
GAD	x					x		
ASI	x					x		
HSP	x					x		
BHS	x							
PID-5	x							
DASS-21	x					x		
SHAPS	x							

PSQI	x					x		
IDAS-II	x					x		
ERQ	x							
CTQ-SF	x							
PCL-5	x							
LEC-5	x							
AUDIT	x					x		
Dr-InC	x					x		
DMQ-R	x					x		
OCDS	x					x		
DAST	x					x		
FTND	x					x		
CUDIT	x					x		
TLFB (timeframe: past 3-months)		x						
TLFB (timeframe: since Lab Visit 1)							x	
CIWA-Ar – Clinician Administered		x	x	x			x	x
MRI Screening Form			x					x
KSS				x (9 times)				
VAS				x (9 times)				
DEQ				x (9 times)				x
POMS				x (4 times)				
Daily Clinical Assessment Form					x			

*CSSRS will be completed as necessary based upon participant reports of suicidal ideation.

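### Suicidal ideation is named as a potentially serious suvorexant effect, but no scheduled suicidality measure is specified from the first dose to the 1-month questionnaires

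*Combined protocol and SAP*

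**What the plan says.** - **The risk.** Section 7.0 (Suvorexant-Related Risks): "Rare but potentially serious side effects include: worsening of depression and increase of suicidal ideation".
- **The schedule.** In Tables 1 and 2 (Appendices) the SSI, with a lifetime timeframe, and the C-SSRS are marked in the Screening column and nowhere else. The footnote reads: "CSSRS will be completed as necessary based upon participant reports of suicidal ideation". The BDI-II and IDAS-II are marked at Screening and at the 1-Month Follow-up.
- **The daily survey.** Section 6.0 (Drug Trial and Monitoring): "The survey will capture: medication adherence (yes/no); timing of pill ingestion; time spent in bed and asleep; medication side-effects; number and timing of alcoholic beverages". Craving, illicit drug use, mood and new medication complete the list. A participant who endorses a side effect other than drowsiness at night is contacted by the study physician. No action is attached to a mood answer.
- **Oversight and response.** Section 11.0: "The PI routinely evaluates for suicidal ideation, behavior and risk", with no visit, frequency or instrument given. It continues: "If suicidality is endorsed by a participant at any point during the assessment or experimental portion of the study, appropriate steps will be taken"; those steps include the C-SSRS. A later bullet says that "participants who show deterioration between assessment and the lab tasks (e.g., increased anxiety, depression, mania, psychosis, or suicidality) may be removed".
- **Termination.** Section 5.0 lists "c) development of suicidal or homicidal ideation requiring hospitalization" among the possible grounds. It also lists (d), psychiatric illness that needs treatment, and (e), clinical deterioration, with a pointer to later text.

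**The concern.** The protocol treats suicidality as serious enough to exclude at entry (Section 4.2(b), SSI of 5 or higher) and lists increased ideation among the drug's potential harms. Once dosing begins, the schedule contains no measure of it. The exposure is one supervised dose and then about 4 weeks of nightly dosing at home, in people with moderate or severe AUD.

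Two things are at stake. The first is participant safety: ideation may come to light late or not at all. The second is what the trial can report. It is meant to inform a larger suvorexant trial, and a low or zero count means little if the question was not put to every participant in the same way. Physician contact follows an endorsed side effect. If one arm has more side effects of any kind, its members will have more conversations in which ideation could emerge, so ascertainment could differ by arm despite blinding.

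**Working it through.** **Step 1. Set the schedule against the named risk** (Tables 1 and 2; Section 6.0).

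| Time | Measures relevant here | Suicidality measure specified? |
|---|---|---|
| Screening | SSI (lifetime), C-SSRS (as needed), BDI-II, IDAS-II | Yes |
| Acute Drug Challenge (first dose) | CIWA-Ar; KSS, VAS, DEQ (9 times each); POMS (4 times) | None described as such |
| Home dosing, 4 weeks | Daily form, 4 × 7 = about 28 mornings | No ideation topic listed; form not in the documents |
| 1-Month Follow-up | BDI-II, IDAS-II and others; no SSI or C-SSRS | Depression measures only, as described |
| Post-treatment EMG visit | TLFB, CIWA-Ar | None |
| Post-treatment fMRI visit (BRAINS group) | CIWA-Ar, MRI form, DEQ | None |

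From the first dose to the 1-month questionnaires, the number of scheduled suicidality instruments is 0.

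**Step 2. Ask what each remaining route needs in order to work.**

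1. Daily side-effect question: the participant must regard ideation as an effect of the capsule and endorse it. Physician contact then follows.
2. Daily mood question: it is asked each morning, but no threshold, reviewer or response is stated.
3. PI evaluation: Section 11.0 introduces it through the PI's experience at screening and at laboratory assessments. No laboratory visit falls between the Acute Drug Challenge and the final part of treatment, so its reach into home dosing is not stated.
4. C-SSRS: it starts after ideation has been reported.

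Routes 1 and 2 are active questions, but general ones. Route 3 is active but unscheduled. Route 4 is a response.

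**Step 3. Check whether the action wording covers home dosing.** One Section 11.0 statement applies at any point in the assessment or experimental portion. The deterioration bullet names the interval from assessment to the lab tasks. Section 5.0(e) points to deterioration text, apparently this bullet. Whether deterioration at home in week 2 falls under it is left to the reader.

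**Step 4. Size, for context only.** The plan gives no figure to reproduce and no incidence for this risk. Input: 40 participants on suvorexant (Section 12.0, Sample Size). Assumption: a true 4-week rate p of 0.1% to 0.5%, kept below the 1–10% that Section 7.0 gives for other side effects because this one is called rare.

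- Chance of at least one case = 1 − (1 − p)^40.
- p = 0.1%: 1 − 0.999^40 = 3.9%.
- p = 0.5%: 1 − 0.995^40 = 18%.
- Zero cases seen, all cases detectable: solve (1 − p)^40 = 0.05, so p = 1 − 0.05^(1/40) = 7.2% (one-sided 95% upper bound).
- If only a fraction s of cases comes to light, zero seen bounds p × s, so the bound on p becomes 7.2%/s. The documents give no basis for s.

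**The case against.** The strongest reply is that participants are not left unasked. A survey every morning covers side effects and mood, and the protocol itself classes ideation as a side effect, so endorsing it would bring a physician review. The PI is said to evaluate suicidality routinely and to oversee suicide assessment during the study. A psychiatrist co-investigator is available through the challenge and the drug trial. Staff monitor side effects and continuing eligibility, and adverse events are reviewed weekly. Entry criteria remove current or past MDD, mania, psychosis and an SSI of 5 or higher, which lowers baseline risk.

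Most of this stands, and it rules out three stronger readings that a reader might infer:

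- *Ideation is found only if a participant volunteers it.* Not supported. Side effects and mood are asked about daily and PI evaluation is stated. The daily form is not reproduced, so it cannot be shown to omit ideation.
- *Ideation leads to termination only if it needs hospitalization.* Not supported. Grounds (d) and (e) in Section 5.0 also apply, and Section 11.0 includes suicidality under deterioration with no hospitalization threshold. The entry criterion, the termination grounds and the response steps serve different purposes and do not contradict each other.
- *A case among the 40 is likely.* Not supported. That needs rates of 1% or more, which sit poorly with a risk called rare beside others at 1–10%.

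It is also fair that the 7.2% bound is mainly a matter of sample size, which better questioning would not change. What the reply does not supply is a scheduled, uniform question during dosing. Availability, weekly review and response steps all act on what is already known.

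**Conclusion.** The point holds as a gap in the specified schedule. The protocol names worsening depression and suicidal ideation as potentially serious drug effects, yet specifies no scheduled suicidality measure from the first dose to the 1-month questionnaires, in either arm. Detection in that window depends on general daily items, of which only endorsed side effects have a stated physician contact, on PI evaluation without a stated schedule or instrument, and on a C-SSRS triggered by report.

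The conclusion rests on Tables 1 and 2 and on the daily topics listed in Section 6.0. It does not depend on the assumed event rates. It would shrink to a request for clarification of the daily survey if that form already contains an ideation item with an escalation route; the visits would still lack a uniform measure. Given the existing safeguards and the entry exclusions, this should be fixed, but it does not show that participants go unmonitored.

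**What to change.** 1. In Tables 1 and 2, schedule the C-SSRS for all participants at the Acute Drug Challenge, before the capsule, and at the post-treatment EMG visit. Each should cover the time since the previous administration (or since Screening, if it was not given then), so that both arms are asked in the same way.
2. State whether the daily form has an ideation item. If it does not, add one and link it to the follow-up process already in Sections 6.0 and 11.0. State who reviews the answers and how soon.
3. Reconcile the two Section 11.0 statements, one reaching any point in the study and the other the interval before the lab tasks, with Section 5.0(c)–(e), so that it is clear whether and how they cover home dosing. The sponsor decides the rule.

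**Cost.** A few minutes at two existing visits with an instrument already in the protocol, one survey item, some extra physician contacts, and an amendment to the text and tables. The survey item is not free: 80 participants × 28 days gives up to 2,240 answers that need timely review, and the protocol describes weekly meetings but no daily review. If that cannot be supported, item 1 alone still gives a uniform measure before the first dose and at the end of treatment, though it would not shorten the delay in finding ideation that arises at home.

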8.0 Data Collection and Management Procedures

- Sources of material from human subjects include: (a) written informed consent, (b) telephone screen form, (c) diagnostic interview, (d) self-report questionnaires, (e) urine drug screen, (f) urine pregnancy test (women only), (g) startle eyeblink data, (h) fMRI data, and (i) EEG data.
- Each subject is given a unique number and there is a password-protected master key database separate from study data linking the subject with the code only accessible to research team members. This file is a password-protected master key database, which links the participant with unique participant codes; it is stored on the password-protected server, and kept separate from study data. The information in this file could be used to *indirectly* identify participants. The record linking participants to the research codes will be destroyed 6 years after completion of the study, thereby anonymizing the data.
- All research materials from participants will be labeled with the unique participant code (not participant name).
- Paper forms with the participant code will be kept in a locked cabinet where only IRB approved key research personnel will have access.
- Data collected during the tasks and fMRI for each participant will be saved with a research identifier number only and stored in computer files without reference to any personally identifiable information. These files will be stored on the lab server. These measurements will be obtained solely for the purposes of research. All research materials will be maintained in strict confidentiality.
- To protect against, or minimize risk associated with participants using smart phones in an unsafe way (attempting to respond to smart phone survey questions while driving a car), participants will be trained to delay responding to the smart phone beeps when it is unsafe (e.g., when driving) or potentially embarrassing (e.g., during a religious service or at the movies). Data collection will be encrypted to prevent access of personally identifiable data should telephones be lost or stolen. The data will be stored on the device itself and can only be accessed by a password system. This means that no one, even the research participant, can see or review entered data.
- When daily clinical assessments are completed, the data will be transferred from the software platform and maintained on secure servers within Center for Human Resource Research (CHRR). CHRR maintains a secure data storage infrastructure. The procedures and infrastructure meet the stringent data protection requirements of the U.S. Census Bureau and the Bureau of Labor Statistics.
- Only IRB approved key research personnel have access to the data. If any member of the research study leaves, his or her access to the network and all files will be removed immediately, thereby terminating access to this file and other files associated with the study.

